7.2.3. Phase 1b Expansion

The Phase 1b part of the study will include 2 expansion arms (pancreatic cancer [N=approximately 15 patients] and ovarian cancer [N=approximately 15 patients]).

Once the safety profile of all doses tested has been characterized and the MTD of combined administration of LY2510924 and durvalumab has been defined in the Phase 1a part of the study, the expansion arms will be initiated.

Treatment in the expansion arms will consist of 1500 mg durvalumab IV on Day 1 of each cycle and LY2510924 SQ daily at the dose determined in the Phase 1a part of the study. A cycle is 28 days.

Continuous evaluation of toxicity in the expansion arms will be performed throughout enrollment in the expansion arms.

7.2.4. DLT-Equivalent Toxicity

A DLT-equivalent toxicity is defined as an AE occurring during Cycle 2 and beyond in Phase 1a that would have met the criteria for a DLT if it had occurred during Cycle 1 or during any cycle in Phase 1b. The DLT-observation period will be extended to Cycle 2 if a DLT-equivalent toxicity is observed during Cycle 2 in any cohort in Phase 1a. For individual patients experiencing a DLT-equivalent toxicity, dose adjustments will be made as outlined in Section 7.2.5. At each interim analysis (as defined in Section 10.10), the rate of DLT-equivalent toxicities will be assessed. If the rate of DLT-equivalent toxicities is unacceptable (for example, a DLT-equivalent toxicity is observed in >33% patients at a given dose level), the data will be reviewed by study investigators and the Lilly CRP or designee in consultation with collaborator and a safety analysis may be triggered. If the findings indicate that a dose level does not have an acceptable safety profile for chronic (Cycle 2 or later) administration, then a lower dose level will be chosen for further investigation. This decision will be documented in writing.

7.2.5. Dose Adjustments, Delays, or Discontinuation from Study Drug

7.2.5.1. LY2510924 Dose Adjustments, Delays, and Discontinuation for Phase 1a and 1b

If a patient has an immune-related AE that requires discontinuation of durvalumab per the dose modification table in [Attachment 11](#), both drugs should be discontinued. Once the immune-related AE has resolved to ≤Grade 1 or baseline, the investigator in consultation with the Lilly physician may resume combination treatment as indicated in [Table CXAD.7.2](#).

7.2.5.1.1. LY2510924 Dose Adjustments and Delays

During Phase 1a, inpatient dose escalation or reduction of LY2510924 is not allowed.

During Phase 1b, 2 dose reductions of LY2510924 are allowed (depending on the starting dose: reduce 1 dose level if available or hold if not available). Reescalation is allowed once at the discretion of the investigator. If Grade 3/4 toxicity attributed to LY2510924 occurs after 2 previous dose reductions, LY2510924 will be discontinued. If patients are discontinued from LY2510924, patients must also be discontinued from durvalumab.

No dose reduction of LY2510924 will occur for myelosuppression. Granulocytosis was observed in patients receiving LY2510924 in the Phase 1 and 2 studies. Management of granulocytosis and nonhematologic toxicity is outlined in [Table CXAD.7.2](#) and in the durvalumab dose-modification tables within [Attachment 11](#).

Table CXAD.7.2. Dose Adjustments of LY2510924

Event	Intervention	Dose Adjustment
Leukocytosis (ANC >75,000/ μ L or leukocytes >100,000/ μ L)	1) Interrupt LY2510924 2) Recheck WBC, ANC every 2 to 3 days until ANC decreases to <50,000/ μ L	Reduce 1 dose level
Injection site reaction, Grade 3	1) Interrupt LY2510924 2) Administer topical treatment as necessary	Reduce 1 dose level
Other nonhematologic toxicities meeting treatment interruption criteria described in Attachment 11	1) Interrupt LY2510924 2) Re-examine patient at least weekly until toxicity improves to \leq Grade 1 and consider restarting treatment according to the durvalumab dose-modification tables (Attachment 11)	Reduce 1 dose level

Abbreviations: ANC = absolute neutrophil cell; WBC = white blood cell.

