7.2.2.1. Dose-Limiting Toxicity Determination and Maximum-Tolerated Dose Definition

A DLT is defined as 1 of the following AEs reported during the Phase 1a DLT observation period, if considered to be definitely, probably, or possibly related to either study regimen by the investigator; and fulfills any 1 of the following criterion using National Cancer Institute (NCI) CTCAE version (v) 4.03:

1. Non-laboratory abnormalities (clinical toxicity):
 - a. Any Grade 4 immune-related AE ([Attachment 10](#))
 - b. Any Grade 4 non-laboratory AE
 - c. Any CTCAE Grade ≥ 3 QT prolongation AE
 - d. Any \geq Grade 3 colitis or noninfectious pneumonitis irrespective of duration
 - e. Any Grade 3 immune-related AE (excluding colitis, QT prolongation, or pneumonitis) ([Attachment 10](#)) that does not downgrade to Grade 2 within 3 days after onset of the event despite optimal medical management including systemic corticosteroids, or does not downgrade to \leq Grade 1 or baseline within 14 days
 - f. Any Grade 2 pneumonitis that does not resolve to \leq Grade 1 within 3 days of the initiation of maximal supportive care, including corticosteroid therapy
 - g. Grade 3 toxicity lasting an extended period of time despite optimal supportive care (for example, nausea, vomiting, and diarrhea lasting >3 days; fatigue lasting >7 days)
2. Laboratory abnormalities:
 - a. Any Grade 3 laboratory value if:
 - i. Medical intervention is required to treat the patient, or
 - ii. Associated with clinically significant symptoms. Examples include but are not limited to, \geq Grade 3 thrombocytopenia if associated with bleeding and requires platelet transfusion, \geq Grade 3 febrile neutropenia, or
 - iii. The abnormality persists for >7 days (excluding amylase and lipase)
 - b. Any Grade 4 laboratory abnormalities
 - c. Liver transaminase elevation $>8 \times$ upper limit of normal (ULN) or total bilirubin $>5 \times$ ULN

Note: Liver test abnormality: For HCC patients and patients with liver metastasis who begin treatment with Grade 2 AST or ALT, if AST or ALT increases by 2-fold greater than baseline and lasts for >7 days

- d. ANC >75,000/ μ L or \geq Grade 3 leukocytosis (leukocytes >100,000/ μ L) of any duration, or leukocytosis/granulocytosis causing clinical symptoms
3. Grade 5 toxicity (that is, death)
4. Any other significant toxicity deemed by the primary investigator and Lilly clinical research personnel to be dose limiting, for example:

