8.1.1. Safety Data Collection and Review

Investigators are responsible for monitoring the safety of patients who have entered into this study and for alerting Lilly or its designee to any event that seems unusual, even if this event may be considered an unanticipated benefit to the patient.

The investigator is responsible for the appropriate medical care of the patient during the study.

The investigator remains responsible for following, through an appropriate health care option, AEs that are serious, considered related to study treatment or the study, or that caused the patient to discontinue before completing the study. The patient should be followed until the event is resolved, the event is no longer considered to be drug-related, the event becomes stable or returns to baseline, a new treatment is initiated for the patient, or the patient dies or is lost to follow-up. Frequency of AE and SAE follow-up evaluation is left to the discretion of the investigator.

The timing of all safety evaluations is shown in the Study Schedule ([Attachment 1](#)). [Table CXAD.8.1](#) presents a summary of AE and SAE reporting guidelines. [Table CXAD.8.1](#) also shows which database or system is used to store AE and SAE data.

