Attachment 1. Protocol CXAD Study Schedule

Baseline, During and Poststudy Assessments

Relative Day Within a Cycle	Baseline		Cycle 1		Cycle 2	Cycle 3-n	Follow-Up			LT FU ^a	Comments
	<28 days	<7 days	1	15	1	1	30 day	60 day	90 day		
Visits							801	802	803	804	
Informed Consent	x										Informed Consent Form signed (prior to performance of any protocol-specific tests/procedures).
Medical History	x										Including alcohol/tobacco use and other relevant habits assessments.
Physical Examination/ Vital Signs	x		x		x		x				Full examination at baseline. Focused examination at other time points. During the study treatment period, occurs within 3 days prior to first day of each cycle. Includes recent height (baseline only), weight, and vital signs (blood pressure, pulse, temperature, and respiratory rate [at baseline and as indicated in Section 7.2.1.2]). See Section 7.2.1.2 for a detailed description of vital sign collection on study.
ECHO	x										Local. ECHOs may be performed on study as clinically indicated to determine LVEF/LV dysfunction and any change in cardiac size or function.

Relative Day Within a Cycle	Baseline		Cycle 1		Cycle 2	Cycle 3-n	Follow-Up				Comments
	<28 days	<7 days	1	15	1	1	30 day	60 day	90 day	LT FU ^a	
Visits							801	802	803	804	
ECG		x	x	x	x						
Obtain ECGs before any associated blood draws.
 
At baseline, triplicate ECG will be obtained, on which QTcF must be <450 ms (calculated from one ECG using Fridericia’s Correction Formula and confirmed with 2 additional ECGs).
 
Cycle 1 Day 1: ECG will be conducted 30 mins post LY2510924 dose.
 
Cycle 1 Day 15 and Cycle 2 Day 1: ECGs will be conducted predose.
 
All ECGs will be done in triplicate.

Concomitant Meds	x		x		x	x	x	x	x		Throughout study as needed.
ECOG Performance Status	x		x		x	x	x	x	x		
HIV, Hepatitis B, and Hepatitis C Testing	x										All tests completed locally. Hepatitis B (HBsAg, Anti-HBc) Hepatitis C (Anti-HCV, HCV RNA)
Hematology		x	x	x	x	x	x	x	x		Local. Complete blood count with differential. If any abnormalities, will follow beyond the 30-day FUP, as clinically indicated

Relative Day Within a Cycle	Baseline		Cycle 1		Cycle 2	Cycle 3-n	Follow-Up				Comments
	<28 days	<7 days	1	15	1	1	30 day	60 day	90 day	LT FU ^a	
Visits							801	802	803	804	

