Serum Chemistry and Liver Function Testing		x	x	x	x	x	x	x	x		Local and central. See Attachment 2 . If any abnormalities, will follow beyond the 30-day FUP, as clinically indicated. To include liver enzyme panel.
Tumor Markers in Blood	x		x		x	x	x	x	x		Local. If applicable to tumor type of the patient (eg, CEA in patients with colorectal cancer or CA125 in patients with ovarian cancer). Obtain predose, if dose administered.
Coagulation		x									Local. Includes prothrombin time, aPTT and INR. As clinically indicated on study and prior to any procedures (eg, tumor biopsy).
Thyroid Function Tests		x	x		x	x	x	x	x		Local. Includes TSH and ft4. Additionally, measure if there is clinical suspicion of an adverse event related to the endocrine system.
Urinalysis		x	x		x	x	x	x	x		Local. See Attachment 2 . If any abnormalities, will follow beyond the 90-day FUP, as clinically indicated.
CTCAE v 4.03 Grading		x	x	x	x	x	x	x	x	x	To be reported only after study eligibility is confirmed. Throughout study as needed. Refer to Section 8.1.2.6 for reporting guidelines. Data on SAEs that occur before the end of trial will be stored in the collection database and the Lilly Safety System.
Urine or Serum Pregnancy Test		x									Local. As clinically indicated while on study.

	Baseline		Cycle 1		Cycle 2	Cycle 3-n	Follow-Up				Comments
	<28 days	<7 days	1	15	1	1	30 day	60 day	90 day	LT FU ^a	
Relative Day Within a Cycle	<28 days	<7 days	1	15	1	1	30 day	60 day	90 day	LT FU ^a	Assessments to be performed at the times stipulated in the table and as clinically required in the management of the patient. All assessments to be performed pre-infusion unless stated otherwise.
Visits							801	802	803	804	
Tumor Tissue		≤3 yrs prior			D7						Central. Core or excisional biopsy of a tumor lesion or a recent biopsy defined by ≤3 years since last documented progression of disease. Patients for whom newly obtained samples cannot be obtained such as in cases of inaccessibility or patient safety concern, an archived specimen can be submitted upon agreement from sponsor. If a fresh biopsy is obtained, an archival specimen (if available) should also be submitted for comparison. On-treatment sample (Cycle 2 Day 7 ±7 days): mandatory for ovarian expansion arm (Phase 1b), optional in Phase 1a and pancreatic expansion arm in Phase 1b.
PK Sampling			D1 & 2	D15 & 16	x	C3, C4, & C6			x		See PK Sampling Attachment 4 for exact timing.

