7.2.5.1.1. LY2510924 Dose Adjustments and Delays

...

Table CXAD.7.2. Dose Adjustments of LY2510924

Event	Intervention	Dose Adjustment
Cytosis -Leukocytosis (ANC >75,000/ μ L or leukocytes >100,000/μL)	1) Interrupt LY2510924 2) Recheck WBC, ANC every 2 to 3 days until ANC decreases to <50,000/ μ L	Reduce 1 dose level
...		

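### The leukocytosis row of Table CXAD.7.2 has two interruption triggers, but its fixed 2-to-3-day rechecks end on ANC alone, so in a narrow group they can end with leukocytes still above 100,000/µL

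*Protocol*

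**What the plan says.** The leukocytosis row of Table CXAD.7.2, in Protocol Section 7.2.5.1.1, has two alternative triggers: ANC above 75,000/µL, "or leukocytes >100,000"/µL. The intervention is to interrupt LY2510924 and then: "Recheck WBC, ANC every 2 to 3 days until ANC decreases to <50,000"/µL. The adjustment is one dose level down; for Phase 1b the text above the table adds "reduce 1 dose level if available or hold if not available". The same text refers granulocytosis to Attachment 11 as well as to the table. Section 7.2.5.1 covers both phases.

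The DLT definition in Section 7.2.2.1, item 2.d, uses the same two limits, and the leukocyte limit counts "of any duration, or leukocytosis/granulocytosis causing clinical symptoms". Section 5.3 and Attachment 13 show that amendment (b) added the leukocyte trigger to the table to match that criterion. The current recheck instruction has no leukocyte value to go with it.

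Routine hematology in Attachment 1 falls on Days 1 and 15 of Cycle 1 and on Day 1 of each later 28-day cycle, with the comment "Complete blood count with differential. If any abnormalities, will follow beyond the 30-day FUP, as clinically indicated". The schedule also carries a general note: "Assessments to be performed at the times stipulated in the table and as clinically required in the management of the patient".

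**The concern.** A row with two ways in should have a way out that covers both. Here WBC is part of every recheck, but only ANC decides when the rechecks end. The leukocyte trigger matters most for patients whose neutrophil share is on the low side, because they reach 100,000 leukocytes before 75,000 neutrophils. An end point based on ANC alone fits that group least well.

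What is at stake is a monitoring rule. The sponsor chose a fixed, close schedule for this event, and it can lapse while leukocytes are at a level that the protocol treats as dose limiting whatever its duration. The gap is at least conceivable for this drug: Section 5.5.1.4 reports that LY2510924 raises circulating lymphocytes as well as neutrophils.

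**Working it through.** There is no figure of the plan's own to reproduce. The check is whether the recheck end point and the leukocyte trigger can both be true at once.

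**Inputs** (Table CXAD.7.2): ANC trigger 75,000/µL; leukocyte trigger 100,000/µL; recheck end point ANC below 50,000/µL.

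**Assumed quantity:** the neutrophil share f at the recheck. The documents give no value at such counts, so it is shown as a range.

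**Formula:** ANC = f × L, where L is the leukocyte count.

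1. *Which trigger fires first.* At L = 100,000, ANC = 100,000 × f. This is below 75,000 when f < 0.75, so the leukocyte trigger comes first for any share under 75%.

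2. *When the end point is met with leukocytes still above the trigger.* This needs f × L < 50,000 with L > 100,000, that is f < 50,000 / L:

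| Leukocytes/µL | End point already met if f is below |
|---|---|
| 100,000 | 0.500 |
| 110,000 | 0.455 |
| 120,000 | 0.417 |
| 150,000 | 0.333 |

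Example: L = 110,000 and f = 0.40 give ANC = 44,000. This patient is interrupted on leukocytes and meets the recheck end point on the same count.

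3. *Leukocytes when ANC reaches 50,000*, from L = 50,000 / f:

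| f | Leukocytes/µL | Above 100,000? |
|---|---|---|
| 0.30 | 166,667 | yes |
| 0.40 | 125,000 | yes |
| 0.45 | 111,111 | yes |
| 0.49 | 102,041 | yes |
| 0.50 | 100,000 | no |
| 0.60 | 83,333 | no |

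4. *How unusual the case is.* The non-neutrophil count is L − ANC, which must exceed 100,000 − 50,000 = 50,000/µL. A patient interrupted at about 100,000 with f = 0.60 is not affected: when ANC reaches 50,000, leukocytes are 83,333 if the share stays constant, or 50,000 + 40,000 = 90,000 if only neutrophils fall.

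5. *After the fix.* If rechecks also require L ≤ 100,000, the overlap disappears at every share. The added condition delays the end of rechecks only when 50,000 / f > 100,000, that is f < 0.50.

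**The case against.** The strongest reply is that the rest of the protocol already protects this patient.

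- **Interruption continues.** Anyone still above 100,000/µL still meets the row's event and its instruction to interrupt. This stands. A reader might infer that the drug would be restarted at a dose-limiting count, but the row directs no restart.
- **Attachment 11 governs resumption.** For a Grade 3 non-immune-mediated reaction it stops treatment until the event is down to Grade 1 or baseline. It allows a restart if the event is at Grade 2 or lower by 7 days, or at Grade 1 or baseline by 14 days; otherwise treatment ends. Section 7.2.2.1 equates leukocytes above 100,000/µL with Grade 3 or worse, so reaching Grade 2 means being back under the trigger. A reader might infer that no recovery rule exists for leukocytes; the documents do not support that. Two limits remain: the rule sets no recheck interval, and the same table exempts laboratory abnormalities judged not clinically significant from dose modification.
- **Follow-up is still required.** Section 8.1.1 has the investigator follow related events until they resolve, stabilize or reach another listed end. A reader might infer that monitoring drops to one count per cycle from Cycle 2. That does not follow: testing as clinically required remains, and the 7- and 14-day rule cannot be applied without counts. But "Frequency of AE and SAE follow-up evaluation is left to the discretion of the investigator", so no fixed interval replaces the one that ended.
- **The patient is hypothetical.** Section 5.6 reports ANC above 25,000 in 2 of 7 patients at 30 mg, and the described signal is granulocytosis. No document shows a neutrophil share below 50% at such counts. This stands and limits the size of the point.
- **The literal reading is harsh.** A sensible investigator would keep checking WBC. Probably so, but the instruction as written does not say it.

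**Conclusion.** The point holds as a minor gap in one safety instruction. The fixed 2-to-3-day rechecks can end with leukocytes above the row's own trigger, and no other section sets a leukocyte end point or a recheck interval for this event. It rests on one assumption, a neutrophil share below 50% when the ANC condition is met, which implies more than 50,000 non-neutrophil leukocytes/µL. That makes it narrow and likely uncommon. It applies in both phases and does not reach any endpoint, error rate or sample size. It is not a finding that patients would be re-treated too early or left unmonitored.

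**What to change.** In the leukocytosis row, keep "Recheck WBC, ANC every 2 to 3 days until ANC decreases to <50,000"/µL and add: and leukocytes are no higher than 100,000/µL. Add one sentence saying that LY2510924 is not resumed until both conditions are met, in addition to the Attachment 11 criteria.

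The change is one table cell and one sentence. It needs no new type of test, since both counts are already in the recheck. The downside is a few more rechecks, and possibly a slightly longer interruption, only in patients whose neutrophil share is below 50%.

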7.2.5.1.2. Discontinuation from LY2510924

Patients with combined elevated AST/ALT AND total bilirubin values meeting discontinuation parameters as described in the DLT definition (Section [7.2.2.1](#)) should be considered for permanent discontinuation based on clinical judgment.

If a patient has a documented CTCAE Grade \geq 3 QT prolongation, the patient should be discontinued from study treatment. The investigator should consider (and may consult with a cardiologist) whether a patient with other evidence of QT prolongation, eg, QT/QTc interval \geq 501 msec and/or a change of >60 msec over baseline, should also be discontinued.

If a patient experiences an AE that requires the patient be discontinued from LY2510924, the patient should also be discontinued from durvalumab.

7.2.5.2. Durvalumab Dose Adjustments, Delays, and Discontinuation for Phase 1a and 1b

Inpatient dose escalation of durvalumab is not allowed in either Phase 1a or 1b.

If a patient has an immune-related AE that requires discontinuation of durvalumab per the dose-modification table in [Attachment 11](#), both drugs should be discontinued. Once the AE has resolved to \leq Grade 1 or baseline, the investigator in consultation with the Lilly physician may resume combination treatment.

For AEs that are considered at least partly due to administration of durvalumab, the following dose adjustment guidance may be applied:

- Treat each of the toxicities with maximum supportive care (including holding the agent suspected of causing the toxicity where required).

- If the symptoms promptly resolve with supportive care, consideration should be given to continuing the same dose of durvalumab along with appropriate continuing supportive care. If medically appropriate, dose modifications are permitted for durvalumab ([Attachment 11](#)).
- All dose modifications should be documented with clear reasoning and documentation of the approach taken.

In addition, there are certain circumstances in which durvalumab should be permanently discontinued.

Based on the mechanism of action of durvalumab leading to T-cell activation and proliferation, there is the possibility of observing immune-related AEs during the conduct of this study. Potential immune-related AEs include immune-mediated enterocolitis, dermatitis, hepatitis, and endocrinopathies. Patients should be monitored for signs and symptoms of immune-related AEs. In the absence of an alternative etiology (eg, infection or progressive disease) signs or symptoms of enterocolitis, dermatitis, hepatitis, and endocrinopathy should be considered to be immune-related.

Dose-modification recommendations and toxicity management guidelines for immune-mediated reactions, for IRRs, and for nonimmune-mediated reactions are detailed in [Attachment 11](#).

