6.2.2. Definitions of Study Periods

Terms used to describe the periods during the study are defined below:

- **Baseline/Screening:** begins when the ICF is signed, and ends at the first study treatment (defined as receiving any study drug); if no study treatment is given, baseline/screening ends with the decision not to enroll. Lasts up to 28 days.
- **Study Period:** The overall study period for Study CXAD begins the day of the first patient's first dose of study treatment and ends at overall study completion (as defined in a bullet below).
 - **Study Treatment Period:** begins with the day of the patient's first study treatment and ends the day the patient and investigator agree that the patient will discontinue study treatment (discontinuation of assigned study drug(s); Section 6.3). Individual patients who enroll in Study CXAD may continue treatment until they have confirmed progressive disease or discontinued study treatment for any other reason.
 - **Post Discontinuation Follow-Up Period:** consists of the following phases:
 - **30-Day Short-Term (Safety) Follow-Up:** begins the day after the patient and the investigator agree that the patient will discontinue study treatment and ends with the short-term follow-up visit, to occur approximately 30 days thereafter.
 - **60-Day Short-Term (Safety) Follow-Up** begins the day after the 30-day follow-up visit and lasts approximately 30 days or approximately 60 days after the patient and the investigator agree that the patient will discontinue study treatment.
 - **90-Day Short-Term (Safety) Follow-Up** begins the day after the 60-day follow-up visit and lasts approximately 30 days or approximately 90 days after the patient and investigator agree that the patient will discontinue study treatment.
 - **Long-term Follow-up** begins the day after 90-day follow-up is completed and continues until the patient's death or end of trial (approximately every 12 weeks \pm 7 days the patient will be contacted).

- **Study Completion** for Study CXAD: occurs after the final analysis (occurring no more than 12 months after last patient enters treatment) and evaluation of the primary objective and secondary objectives have been performed. Investigators will continue to follow the Schedule of Events ([Attachment 1](#)) for all patients, until notified by Lilly that study completion has occurred.

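### The restart sentence in Protocol 7.2.5.2 is not limited to the immune-related events for which Attachment 11 allows restart

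*Protocol*

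**What the plan says.** In Protocol 7.2.5.2 the trigger is: "If a patient has an immune-related AE that requires discontinuation of durvalumab per the dose-modification table in" Attachment 11. In that case both drugs are discontinued. The next sentence gives the way back: when the AE has resolved to no worse than "Grade 1 or baseline, the investigator in consultation with the Lilly physician may resume combination treatment". Those are its only two conditions.

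Later in the same section comes "In addition, there are certain circumstances in which durvalumab should be permanently discontinued", without naming the circumstances. The section closes with "Dose-modification recommendations and toxicity management guidelines for immune-mediated reactions, for IRRs, and for nonimmune-mediated reactions are detailed in" Attachment 11.

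Section 7.2.5.1 has a parallel sentence with one difference: the investigator "may resume combination treatment as indicated in" Table CXAD.7.2. The third row of that table covers other nonhematologic toxicities that meet Attachment 11's interruption criteria, and tells the site to "consider restarting treatment according to the durvalumab dose-modification tables".

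Attachment 11 mostly keeps two verbs apart. It uses *hold* for temporary stops and *permanently discontinue* for nearly all final ones.

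**The concern.** The restart sentence is attached to events that require discontinuation under Attachment 11, and nearly all immune-related discontinuations there are permanent. A body-text permission therefore disagrees with the safety table it cites. A site relying on the body text could think it open to restart both drugs after a severe immune-related event has settled, or while the patient is still on a steroid taper. Nothing states which wording governs. At stake are re-exposure to a checkpoint inhibitor after events such as severe pneumonitis or colitis, and uniform handling across sites in a trial whose primary endpoint is safety.

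**Working it through.** No arithmetic applies beyond counting. The check sets 7.2.5.2 beside the specific immune-mediated categories of Attachment 11.

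| Category | Permanent discontinuation | Steroid taper completed before restart, Grade 2 |
|---|---|---|
| Pneumonitis/ILD | Grades 3 and 4 | Yes |
| Diarrhea/enterocolitis | Grades 3 and 4 | Yes |
| Hepatitis | Grade 4; any Hy's law case; Grade 3 not recovered within 14 days | Yes |
| Nephritis | Grades 3 and 4 | Yes |
| Rash | Grade 4; Grade 3 not improved within 30 days | Yes |
| Endocrinopathy | None (held, even at Grades 3-4) | Yes, except replacement steroids at prednisone 10 mg/day or less |
| Neurotoxicity | Grade 4; Grade 3 not resolved within 30 days | Yes |
| Neuromotor syndromes | Grade 4; Grades 2-3 not resolved within 30 days, or with respiratory insufficiency or autonomic instability | Not stated |

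**Reading 1: discontinuation is meant literally.**
- Categories with at least one permanent rule: 8 − 1 (endocrinopathy) = 7.
- In pneumonitis, enterocolitis and nephritis the rule covers Grade 3 with no time limit. The Hy's law rule and the neuromotor rule for respiratory or autonomic signs also have no time limit.
- Attachment 11 adds two general permanent rules: failure to bring steroids down to prednisone 10 mg/day within 12 weeks of the last dose, and recurrence of a Grade 3 treatment-related AE after dosing resumes.
- One exception runs the other way: Grade 3-4 inflammation attributed to local tumor response does not require discontinuation.
- Example: Grade 3 pneumonitis resolves to Grade 1. Attachment 11 says never restart. The 7.2.5.2 sentence says restart may follow consultation.
- Second example: Grade 3 rash reaches Grade 1 after more than 30 days. The two texts disagree in the same way.

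**Reading 2: a hold was meant.** This is the likelier intent. Attachment 11 uses *hold* for temporary stops, and under 6.2.2 the treatment period "ends the day the patient and investigator agree that the patient will discontinue study treatment", so discontinuation elsewhere means the end of treatment.
- Categories with a taper condition at Grade 2: 8 − 1 (neuromotor) = 7. Attachment 11's general Grade 2 rule has the same condition, as do Grade 3 hepatitis within its 8 × ULN (transaminases) and 5 × ULN (bilirubin) limits and Grade 3-4 endocrinopathy.
- The condition is not universal. It is not stated for Grade 3 rash, Grade 3 neurotoxicity or neuromotor syndromes.
- The omission matters because grade recovers before the taper ends. For Grade 2 pneumonitis and enterocolitis, tapering starts once the patient is improving and takes at least 28 days, a full treatment cycle. Grade 1 can therefore be reached with weeks of steroid still to run. Section 7.5 does not close this gap, because it allows immunosuppressives for managing product-related AEs.

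The two sevens are different sets under alternative readings, and should not be added.

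**The case against.** The strongest defense is that the protocol, read as a whole, already contains the limits. The 7.2.5.2 trigger cites Attachment 11, the section acknowledges permanent discontinuation, and it closes by pointing to the attachment. Restart is permissive and needs the sponsor's physician. Section 7.2.5.1 allows restart only through Table CXAD.7.2, whose relevant row is confined to interruption criteria, so a permanently discontinued event has no route back there. Section 6.2 and the synopsis stop both drugs with no resumption clause. To re-treat after Grade 3 pneumonitis, the site and the sponsor would both have to disregard the table that the sentence cites.

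This stands as mitigation. It does not cure the wording. The statement on permanent discontinuation names no events and does not qualify the restart sentence. The closing pointer describes Attachment 11 as recommendations and guidelines. The Table CXAD.7.2 limit belongs to 7.2.5.1 and is missing from 7.2.5.2. The sponsor's physician works from the same text.

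A second objection is that the two defects cannot both hold: literal discontinuation excludes Grade 2 holds, and a hold excludes permanent discontinuations. That is right, and they are put here as alternatives. On the hold reading the fault is an omission, not a contradiction, since recovery to Grade 1 can be one necessary condition with the others left to the table.

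**Conclusion.** The point holds and should be corrected at the next amendment. On the literal reading, the sentence contradicts Attachment 11 in seven of eight categories. On the hold reading, it omits a restart condition that applies at Grade 2 in seven of eight. The conclusion rests on the wording alone, and the documents do not support an estimate of affected patients.

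A reader might infer more, in three ways:
- **That the protocol directs re-treatment after severe pneumonitis or colitis.** It does not. The sentence is permissive, requires consultation, and cites a table that forbids it.
- **That every held event needs a completed taper.** Attachment 11 does not say so, as the exceptions above show.
- **That both drugs should be held whenever Attachment 11 holds durvalumab.** The 7.2.5.2 sentence concerns immune-related AEs only. Attachment 11 handles non-immune reactions in a separate table, and the third row of Table CXAD.7.2 covers only nonhematologic toxicities.

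Two neighboring matters are separate. Some Attachment 11 entries say only to discontinue: transaminases above 8 × ULN or bilirubin above 5 × ULN, bullous rash, and the Grade 3 and 4 non-immune entries. Section 7.2.5.1.2 says that patients with combined liver elevations meeting the DLT parameters "should be considered for permanent discontinuation based on clinical judgment". Clarifying these is optional.

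**What to change.** Keep the first sentence of 7.2.5.2 (both drugs stop). Replace the restart sentence there, and align 7.2.5.1, with:

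> For an immune-related AE, combination treatment may be resumed, in consultation with the Lilly physician, only where Attachment 11 permits resumption and its conditions are met (including completion of steroid taper where required). If Attachment 11 requires permanent discontinuation for the immune-related AE, neither drug may be resumed.

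Keep the reference to Table CXAD.7.2 in 7.2.5.1 for the LY2510924 dose on restart. Leave the handling of non-immune reactions unchanged. The change then adds no LY2510924 holds for those events, which could otherwise count against the 75%-of-doses rule for DLT evaluability.

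The cost is one sentence replaced by two in each of two sections. Sites already following Attachment 11 would change nothing. Design, sample size and analysis methods stay as they are.
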